2.3.2 Randomization

Cohort 1 of this study is an open label study. Subject randomization is not applicable for this part of the study.

Subjects that are determined to be eligible for treatment in Cohort 2 will be randomized in a 1:2 ratio to one of the following treatment arms.

- ARM A: A-101 40% Solution; No medical abrasion to the Target DPN Lesions Treatment Days 1, 15 and 29
- ARM B: A-101 40% Solution applied after medically abrading the Target DPN Lesions; Treatment Days 1, 15 and 29

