2.4.2 Evaluations – Efficacy

2.4.2.1 Physician's DPN Lesion Assessment

The Physician's DPN Lesion Assessment is the investigator's assessment of the severity of the Target DPN Lesion at a particular time point. The investigator should NOT refer to any other assessments to assist with these assessments.

At Visits 1, 2, 3 (cohort 2 ONLY), 4 (cohort 1 ONLY), 5 (cohort 2 ONLY), 6, 7 and 8, the investigator will assess the Target DPN Lesion using the scale below and report the one integer that best describes the severity of the Target DPN Lesion. At Visit 2, and if appropriate at Visit 4 for cohort 1 subjects or Visit 3 and Visit 5 for cohort 2 subjects, the investigator must complete the Physician's DPN Lesion Assessment prior to the study medication treatment.

Table 3: Physician's DPN Lesion Assessment Definitions

Grade	Descriptor
0	Clear: no visible DPN lesion;
1	Near Clear: a slightly visible DPN lesion; lesion may be macular
2	Small: a visible DPN lesion with a diameter of less than 3 mm
3	Large: a visible DPN lesion that is elevated with a diameter of $\geq 3 \text{ mm}$

At Visit 1 and Visit 2, for the subject to be eligible for enrollment to the study the identified DPN lesions must have a Physician's Lesion Assessment of grade ≥ 2 .

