3.2 ANALYSIS POPULATION AND DISPOSITION OF SUBJECTS

3.2.1 Data Sets Analyzed

Per-protocol (PP) analysis set

All treated subjects completing all treatment visits and Visit 8 with no major protocol violations.

Intent-to-Treat (ITT) analysis set

Intent-to-Treat (ITT) analysis set includes all treated subjects with at least one post-baseline visit.

Safety analysis set

The Safety Analysis Set includes all treated subjects.

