3.6.1 Physician's Leasion Assessment (PLA) Analyses

PLA related parameters will be summarized at lesion level and at subject level.

At each visit or applicable visit, the following analyses will be performed:

• Descriptive statistics will be provided for the per-subject mean change from baseline in PLA for each post-baseline scheduled visit separately for the PP population.

- Descriptive statistics will be provided for the per-subject mean change from baseline in PLA for each post-baseline scheduled visit separately for the ITT population.
- The number and percent of subjects having all lesions with PLA score of 0 will be provided for each post-baseline scheduled visit separately (PP population).
- The number and percent of subjects having all lesions with PLA score <= 1 will be provided for each post-baseline scheduled visit separately (PP population).

The following treatment group comparisons will be performed for PLA endpoints from Cohort 2:

- Tretment group comparisons will be made for the change from baseline in per-subject mean PLA score at each post-baseline scheduled visit for the PP population. These comparisons will be made using a repeated measures mixed model where treatment group and time (visit) are included as class variables and baseline per-stubject mean PLA score and number of treated lesions will be included as continuous covariates. The per-subject PLA measures over time will be treated as repeated measures by including subject as a random effect. An unstructured variance covariance matrix will be assumed. If the model experiences convergence issues with the unstructured variance covariance assumption, then a compound symmetric assumption will be used. The difference in least square means for the treatment groups along with corresponding 95% confidence intervals and p-values will be provided for each of the scheduled visits. A plot of the treatment group least square means (and 95% confidence intervals) across time (visit) will be provided.
- Tretment group comparisons will be made for the change from baseline in per-subject mean PLA score at each post-baseline scheduled visit for the ITT population using LOCF for missing data. The model for analysis and output will match that of the PP population analysis and output described above.

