- A logistic regression will be used to make treatment comparions in the proportion of subjects having all lesions with PLA score of 0 (PP population). This analysis will be performed at each scheduled visit separately. This model will include a class variable for treatment group as well as baseline per-subject mean PLA score and number of treated lesions as a continuous covariate. Model based odds ratios, corresponding 95% confidence intervals and p-values will be provided at each scheduled visit.
- Similarly, a logistic regression will be used to make treatment comparions in the proportion of subjects having all lesions with PLA score of <= 1. This model and output will be the same as described for the PLA score = 0 analysis.

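### The per-visit responder logistic regressions on a planned 8 v 16 subjects name no method for separation, so an arm with no responders or all responders gives no finite odds ratio

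*SAP*

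**What the plan says.** SAP 3.6.1 sets out the responder comparison for Cohort 2: "A logistic regression will be used to make treatment comparions in the proportion of subjects having all lesions with PLA score of 0", in the per-protocol population and separately at each scheduled visit. On the terms: "This model will include a class variable for treatment group as well as baseline per-subject mean PLA score and number of treated lesions". On the output: "Model based odds ratios, corresponding 95% confidence intervals and p-values will be provided at each scheduled visit". The second endpoint, all lesions at PLA 1 or below, follows the same plan: "This model and output will be the same as described for the PLA score = 0 analysis".

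On numbers, SAP 1.1 gives Cohort 2 a total of 24 subjects. SAP 2.3.2 says that they "will be randomized in a 1:2 ratio to one of the following treatment arms", with the no-abrasion arm (A) named first. The per-protocol set in SAP 3.2.1 is: "All treated subjects completing all treatment visits and Visit 8 with no major protocol violations".

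SAP 3.6.1 does foresee a fitting failure, but only for the mixed model: "If the model experiences convergence issues with the unstructured variance covariance assumption, then a compound symmetric assumption will be used". No corresponding rule exists for the logistic models in either document. Protocol 12.2 limits the analyses to visits where they are possible, without saying what replaces them elsewhere. SAP section 4 keeps the responder models and adds the number of treated lesions as a covariate.

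**The concern.** If one arm has no responders, or only responders, the likelihood keeps rising as the treatment coefficient moves towards infinity. No finite odds ratio exists and the Wald interval is unusable. The Wald p-value goes to 1 even when the arms differ greatly, because the standard error grows faster than the estimate. The covariates cannot repair this.

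The setting makes sparse cells plausible. Every target lesion must be grade 2 or higher at entry, so all subjects start as non-responders on both endpoints. A responder needs every treated lesion to reach the threshold, and the first comparison comes at Day 15 after one treatment visit.

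The SAP does not say which test supplies the p-value. At an affected visit the result therefore depends on a choice that could be made after the data are seen. SAP section 4 also drops the hypothesis tests on the percentage of lesions clear and clear or near-clear. The responder models are then the only inferential analyses of clearance left, and Protocol 12.1 intends the results to inform the sample size of later studies.

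**Working it through.** **Inputs.** Cohort 2: 24 subjects (SAP 1.1). Ratio 1:2 (SAP 2.3.2), so 24 × 1/3 = 8 in Arm A and 24 × 2/3 = 16 in Arm B. The documents give no responder rates, power or effect size, so there is no plan figure to reproduce and all rates below are assumptions.

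**Number of fits.** The Cohort 2 schedule (SAP Table 2) has PLA at Visits 3 to 8, which is six visits. SAP 2.4.2.1 instead lists "At Visits 1, 2, 3 (cohort 2 ONLY), 4 (cohort 1 ONLY), 5 (cohort 2 ONLY), 6, 7 and 8", which leaves out Visit 4 for Cohort 2 and gives five. Two endpoints × 5 or 6 visits = 10 or 12 fits.

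**Chance of an empty or full arm, per fit.** With responder rates pA and pB:

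P = 1 − [1 − (1−pA)^nA − pA^nA] × [1 − (1−pB)^nB − pB^nB]

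Example at 10% in both arms, 8 v 16: 0.9^8 = 0.430 and 0.9^16 = 0.185, so P = 1 − 0.570 × 0.815 = 0.54.

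| Rate in both arms | 8 v 16 | 7 v 14 (assumed per-protocol loss) |
|---|---|---|
| 5% | 81% | 85% |
| 10% | 54% | 60% |
| 20% | 19% | 24% |
| 30% | 6% | 9% |
| 40% | 1.8% | 3% |
| 50% | 0.8% | 1.6% |

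The figures mirror at high rates (80% behaves as 20%). With unequal rates (Arm A/Arm B) at 8 v 16: 43% at 10%/40%, 17% at 20%/50%, 19% at 50%/90%.

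**Counting separation on the covariates too.** This used simulated trials with 1 to 4 lesions (equally likely, or weighted 0.1/0.1/0.2/0.6) and baseline grades 2 or 3 equally likely, each checked by linear programming. The chance that some coefficient is not finite is 84–89%, 58–65%, 21–30%, 7–11%, 2–4% and 1–2% for the six rates in the table.

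**From lesion clearance to subject response.** Assume 30% of lesions clear with within-subject correlation 0.3, beta-binomial. The parameters sum to 0.7/0.3 = 2.333, with first parameter 0.3 × 2.333 = 0.7. The chance that all lesions are clear is then:

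- 1 lesion: 0.300
- 2 lesions: 0.300 × 1.7/3.333 = 0.153
- 3 lesions: 0.153 × 2.7/4.333 = 0.095
- 4 lesions: 0.095 × 3.7/5.333 = 0.066

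Averaged over the two lesion-count mixes, the responder rate is 10% (weighted) or 15% (equal). The formula above then gives 52% or 31% per fit. At 40% of lesions clear, the responder rate is 16–23% and the chance 14–28%. At 50% of lesions clear, the chance is 5–12%.

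**What the planned model would print, 0/8 v 8/16 (treatment only).**

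- Newton maximum likelihood with Wald test: p = 0.794, 0.989 and 0.999 after 8, 15 and 20 iterations (SE 35, 1,166 and 14,210).
- Likelihood ratio: the fitted log-likelihood tends to 16 ln(1/2) = −11.09. The null is 8 ln(1/3) + 16 ln(2/3) = −15.28. The statistic is 8.37 and p = 0.0038.
- Firth: in a 2×2 table this adds one half to each cell, so OR = (8.5/8.5)/(0.5/8.5) = 17.0. Profile 95% CI 1.6 to 2,330, p = 0.013.
- Fisher's exact: p = 0.022.

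**Other tables (treatment only).** For 0/8 v 5/16 the methods fall on both sides of the SAP's 0.05 level: likelihood ratio 0.030, Firth 0.093 (OR 8.1), Fisher 0.13, Wald 0.81 or more. For 4/8 v 16/16, possible for the PLA 1-or-below endpoint, Firth gives OR (16.5/0.5)/(4.5/4.5) = 33.0, p = 0.004. Fisher gives 0.007 and Wald 0.71 to 0.998.

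**With the SAP covariates.** On one simulated data set with 0/8 v 5/16 and both covariates in the model, the treatment log odds ratio was 4.6, 11.6 and 19.6 after 5, 12 and 20 iterations. It does not settle.

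**The case against.** The strongest reply is that little hangs on these models. They are secondary, SAP section 3 describes the plan as mainly descriptive, and SAP section 4 says that a separate DPN indication is no longer pursued and an abbreviated report will be written. Responder counts by arm are tabulated (SAP 3.1 and 3.6.1), so a reader would still see 0/8 against 8/16. This limits the severity. It does not make the promised odds ratio, interval and p-value obtainable.

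Second, the large percentages describe non-finite estimates, not changed verdicts. At a 5% rate, 0.95^24 = 29 of the 81 points are visits with no responder in either arm, where there is nothing to compare. At 10% it is 8 of the 54. Many remaining low-rate tables are unremarkable by any method: 0/8 v 1/16 gives 0.36 by likelihood ratio, 0.76 by Firth and 1.0 by Fisher. With equal rates, the chance per fit of a separated table that reaches p < 0.05 by likelihood ratio, Firth or Fisher is 2.6% at a 5% rate, 4.2% at 10%, 4.8% at 20% and 1.5% at 40%. This stands. The harm is concentrated where the arms truly differ: 36% per fit at 10%/40% and 16% at 20%/50%.

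Third, the Protocol's allowance for visits where analysis is not possible lets a fit be skipped. It names no alternative, and the later SAP sentence promises output at each visit.

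Fourth, the SAP gives no block size, so the split could be 9 v 15. That hardly alters the result: 51% instead of 54% at a 10% rate, and 16% instead of 19% at 20%.

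**Conclusion.** The concern holds. On a planned 8 v 16, reduced further by any per-protocol exclusions, the SAP promises estimates that ordinary maximum likelihood cannot supply when an arm is empty or full, and it leaves the p-value at those visits to an unstated choice. How often this happens depends on responder rates that the documents do not give. It is common below about 20% or above about 80%, and rare near 50%. Because all subjects start as non-responders, the PLA = 0 endpoint at early visits looks most exposed; that is inference, not a documented rate. The worked p-values omit the two covariates and illustrate the size of the disagreement between methods. The primary mixed model is not affected. This should be fixed, but it does not threaten the main result.

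**What to change.** Add to SAP 3.6.1, for both responder endpoints at every visit: the stated models will be fitted by Firth penalised likelihood, with profile-likelihood 95% confidence intervals and penalised likelihood-ratio p-values. At any visit where no subject, or every subject, across both arms is a responder, only counts will be shown. Exact logistic regression would also serve, and Fisher's exact test may be added as a check.

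A rule invoked only after separation would close the gap too. Using one method throughout is simpler and keeps the visits comparable. State at the same time whether Visit 4 is a PLA visit for Cohort 2, since SAP 2.4.2.1 and SAP Table 2 disagree.

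The cost is one sentence and one model option, with no new data. Odds ratios are shrunk slightly towards 1, and intervals remain very wide at this sample size.

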3.6.2 Subject Self Assessment (SSA) Analyses

Descriptive statistics will be provided for the per-subject mean change from baseline in the subject self-assessment scale for each post-baseline scheduled visit separately.

3.7 SAFETY ANALYSIS

The safety and tolerability of the investigational products will be determined by LSR, reported AEs, laboratory tests and vital signs. The Safety analysis set with actual treatment received (as opposed to randomized treatment) will be used for all safety summaries, unless otherwise specified.

3.7.1 Study Drug Exposure And Compliance

Duration of treatment (Last study treatment application date – First study treatment application date + 1) will be summarized descriptively using the Safety analysis set. Number and percentage of subjects at each visit will be summarized by the number of target/non-target lesions being treated. In addition, number and percentage of subjects with re-treatment will be summarized for the applicable visits (Visit 4 for cohort 1 subjects, and Visits 3 and 5 for cohort 2 subjects).

3.7.2 Local Skin Reaction (LSR)

For each visit, all predefined signs and symptoms at pre-medication and post-medication will be summarized by maximum severity cross all lesions for a subject. Number and percentage of subjects with grades 1, 2, 3, 4 will be tabulated for each sign (investigator)/symptom (subject) and at each visit. In addition, the maximum severity for each sign and symptom will also summarized cross all visits. Similar summaries will be presented for lesions. That is, number and percentage of lesions with grades 1, 2, 3, 4 will be tabulated for each sign and symptom at each visit and over all visits.

For treatment visits (ie, Visits 2 and 4 [cohort 1] and Visits 2, 3 and 5 [cohort 2]), for each sign (investigator assessment: Erythema, Edema, Scaling/dryness, Vesicles/bullae) or symptom (subject assessment: Stinging/burning, Pruritus [itch]) will be summarized using shift table. Severity grade shift from pre-medication to post-medication will be analyzed. Number and percentage of lesions with shifts will be presented. Number of treated lesions will be used as the denominator for percentage calculation.

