9.1. Local Skin Reactions (LSR)

The LSR assessment is the investigator's assessment of the signs and the subject's assessment of the symptoms associated with irritation at each Target DPN Lesion site, which includes the Target DPN Lesion and the area immediately surrounding the Target DPN Lesion.

Local Skin Reactions:

- Signs (assessed by the investigator):
 - Erythema
 - Edema
 - Scaling/dryness
 - Vesicles/bullae
 - Crusting
 - Erosion
 - Ulceration
 - Post-inflammatory hyper-pigmentation
 - Post-inflammatory hypo-pigmentation (does not include the superficial transient skin blanching/whitening related to the action of the study medications)
 - Atrophy
 - Scarring.
- Symptoms (assessed by the subject):
 - Stinging/burning
 - Pruritus (itch).

At Visits 2-8, the investigator and the subject will evaluate the LSR signs and the LSR symptoms at each Target DPN Lesion site respectively.

The investigator will assess the LSR signs as follows:

- Visits 2 and 4 (cohort 1) and Visits 2, 3 and 5 (cohort 2):
 - For each Target DPN Lesion site report the severity for all signs prior to any study medication treatment

- For every treated Target DPN Lesion site, 20 (\pm 4) minutes after the Treatment Completion Time, report the severity for the following signs:
 - Erythema
 - Edema
 - Scaling/dryness
 - Vesicles/bullae
- Visits 3 and 5-8 (cohort 1) and Visits 4 and 6-8 (cohort 2):
 - For each Target DPN Lesion site, report the severity for all signs.

The subject will assess the LSR symptoms as follows:

- Visits 2 and 4 (cohort 1) and Visits 2, Visit 3 and Visit 5 (cohort 2):
 - For each Target DPN Lesion site report the average of the severity over the previous 24 hours for all symptoms prior to any study medication treatment
 - For every treated Target DPN Lesion site, 10 (\pm 4) minutes after the Treatment Completion Time, report the average of the severity of the LSR for all symptoms since completion of the study medication treatment.
- Visits 3 and 5-8 (cohort 1) and Visits 4 and 6-8 (cohort 2):
 - For each Target DPN Lesion site, report the average of the severity over the previous 24 hours for all symptoms.

Both the subject and the study staff member will initial and date the source document to indicate the subject performed the LSR for symptoms as instructed. The staff member must not influence the subject's assessment.

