The investigator should report the one integer that best describes the severity of each LSR sign for each Target Lesion site using the scale below. Each subject should report the one integer that best describes the severity of each LSR symptom for each Target Lesion site using the scale below:

Table 6 Grading of Local Skin Reactions

Local Skin Reactions	
Grade	Descriptor
0	None
1	Mild
2	Moderate
3	Severe

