2.3.3 Administration of Treatment

The study medications are for external, topical use on the DPN Target Lesions on the appropriate study subject only.

The treating investigator performing the study medication treatments must comply with the study medication handling warnings. In cohort 1, the treating physician will apply the A-101 Solution 40% to each DPN Target Lesion at Visit 2 and at Visit 4, if applicable.

At Visit 4, any Target Lesion that has a Physician DPN Lesion Assessment grade of >0 and ONLY DPN Target Lesions that have a Physician DPN Lesion Assessment grade of >0, must receive study medication treatment UNLESS either of the following criteria apply to the DPN Target Lesion:

- The DPN Target Lesion has a Visit 4 pre-treatment LSR grade of 3 (severe) for any sign or symptom AND the grade has increased compared to the Visit 3
- The DPN Target Lesion is, in the investigator's opinion, not appropriate for a retreatment (the investigator must note the reason on the subject's Comments CRF page).

In cohort 2, for those subjects randomized to ARM B, the treating physician will medically abrade the Target DPN Lesion prior to apply the A-101 study medication. All subjects in cohort 2 will be allowed to have up to 3 treatment applications of the A-101 study medication. If subjects meet the criteria as outlined above, subjects in cohort 2 may receive 2 additional study medication applications at Visit 3 (Day 15) and Visit 5 (Day 29).

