2.4.3 Evaluations – Safety

2.4.3.1 Local Skin Reaction (LSR)

The LSR assessment is the investigator's assessment of the signs and the subject's assessment of the symptoms associated with irritation at each Target DPN Lesion site, which includes the Target DPN Lesion and the area immediately surrounding the Target DPN Lesion.

At Visits 2-8, the investigator and the subject will evaluate the LSR signs and the LSR symptoms at each Target DPN Lesion site respectively.

The investigator will assess the LSR signs as follows:

- Visits 2 and 4 (cohort 1) and Visits 2, 3 and 5 (cohort 2):
 - For each Target DPN Lesion site report the severity for all signs prior to any study medication treatment
 - For every treated Target DPN Lesion site, 20 (±4) minutes after the Treatment Completion Time, report the severity for the following signs:
 - Erythema
 - Edema
 - Scaling/dryness
 - Vesicles/bullae
- Visits 3 and 5-8 (cohort 1) and Visits 4 and 6-8 (cohort 2):
 - For each Target DPN Lesion site, report the severity for all signs.

The subject will assess the LSR symptoms as follows:

• Visits 2 and 4 (cohort 1) and Visits 2, Visit 3 and Visit 5 (cohort 2):

- For each Target DPN Lesion site report the average of the severity over the previous 24 hours for all symptoms prior to any study medication treatment.
- For every treated Target DPN Lesion site, 10 (±4) minutes after the Treatment Completion Time, report the average of the severity of the LSR for all symptoms since completion of the study medication treatment.
- Visits 3 and 5-8 (cohort 1) and Visits 4 and 6-8 (cohort 2):
 - For each Target DPN Lesion site, report the average of the severity over the previous 24 hours for all symptoms.

Both the subject and the study staff member will initial and date the source document to indicate the subject performed the LSR for symptoms as instructed. The staff member must not influence the subject's assessment.

The investigator should report the one integer that best describes the severity of each LSR sign for each Target Lesion site using the scale below. Each subject should report the one integer that best describes the severity of each LSR symptom for each Target Lesion site using the scale below:

Table 5: Grading of Local Skin Reactions

Grade	Descriptor
0	None
1	Mild
2	Moderate
3	Severe

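### SAP 3.7.2 tabulates local skin reactions as grades 1 to 4 on a 0-to-3 scale, and its all-visit maximum gives pigment change, atrophy and scarring no comparison with baseline

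*SAP*

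**What the plan says.** **Scale.** Protocol section 9.1 ("Table 6 Grading of Local Skin Reactions") and SAP section 2.4.3.1 ("Table 5: Grading of Local Skin Reactions") give the same four grades: 0 none, 1 mild, 2 moderate, 3 severe. The retreatment rule in SAP 2.3.3 uses the same top grade: "The DPN Target Lesion has a Visit 4 pre-treatment LSR grade of 3 (severe) for any sign or symptom".

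**Tabulation.** SAP 3.7.2 uses a different list, first for subjects, "Number and percentage of subjects with grades 1, 2, 3, 4 will be tabulated", and then for lesions, "number and percentage of lesions with grades 1, 2, 3, 4 will be tabulated for each sign and symptom at each visit and over all" of them.

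**Readings that feed the tables.** Within a visit, "all predefined signs and symptoms at pre-medication and post-medication will be summarized by maximum severity cross all lesions for a subject". Across the study, "the maximum severity for each sign and symptom will also summarized cross all visits".

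**When LSRs are scored.** Visits 2 to 8. At every treatment visit, including Visit 2, the investigator scores the full list of signs before drug is applied: "For each Target DPN Lesion site report the severity for all signs prior to any study medication treatment". The 20-minute reading after treatment covers four signs only: erythema, edema, scaling/dryness and vesicles/bullae.

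**Comparison with an earlier grade.** SAP 3.7.2 plans shift tables from the pre-medication to the post-medication reading within each treatment visit, for those four signs and for the two symptoms (stinging/burning and itch). It plans no others.

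**The concern.** Safety is part of the primary objective. The protocol introduction names pigment change and scarring as the main drawbacks of existing treatments in darker skin. The LSR tables are the systematic, graded record of those outcomes out to Visit 8 (Day 106). The adverse event tables do not replace them, because SAP 3.7.3 closes the treatment-emergent window 30 days after the last treatment.

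Two things in SAP 3.7.2 weaken that record. The list of grades does not match the instrument. And the study-wide summary is a maximum with no reference to what was present before the first application. For a sign such as hyperpigmentation, a subject who enters with a mild grade and never changes would appear in that summary in the same row as a subject whose mild grade arose after treatment.

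**Working it through.** **1. Grade lists compared.**

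| Source | Grades |
|---|---|
| SAP Table 5 and Protocol Table 6 | 0, 1, 2, 3 |
| SAP 3.7.2, subjects | 1, 2, 3, 4 |
| SAP 3.7.2, lesions | 1, 2, 3, 4 |

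Listed but not on the scale: 4. On the scale but not listed: 0. The SAP states no recoding.

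**2. Does the all-visit maximum include the Visit 2 pre-medication score?** LSR visits start at Visit 2. SAP 3.7.2 names pre-medication readings as input and sets no lower limit on visits for the maximum. Section 3.6.1 limits the efficacy summaries to post-baseline visits; the LSR section has no such wording. So the plain reading includes the score, although no sentence says so outright. For pigment change, atrophy and scarring the pre-medication score is the only Visit 2 value, because the 20-minute reading omits these signs.

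**3. Is there any within-lesion comparison with baseline for these four signs?** The shift tables omit them. The by-visit tables show the Visit 2 pre-medication distribution and later distributions, but only as separate frequencies. By contrast, SAP 3.7.4 and 3.7.5 give laboratory tests and vital signs a change from baseline.

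**4. Do the entry criteria rule out a pre-existing sign?** Exclusion 3 removes subjects with earlier hypertrophic scarring or keloid. Exclusion 4 removes those whose hyperpigmentation lasted over 1 year. Target lesions must be previously untreated and free of inflammation or irritation, and exclusion 9 lets the investigator reject interfering skin disease. Shorter-lasting hyperpigmentation, hypopigmentation, atrophy and other scars remain possible.

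**5. Weight of one subject.** SAP 3.1 reports by Cohort 1 skin type and Cohort 2 arm.
- Cohort 2: 24 randomised 1:2 gives 24 × 1/3 = 8 in Arm A and 24 × 2/3 = 16 in Arm B. One subject is 1/8 = 12.5 points or 1/16 = 6.25 points.
- Cohort 1: 6 per skin type, so one subject is 1/6 = 16.7 points.

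**6. Illustration over a range.** Let b be the share of subjects with grade 1 or higher before treatment, and e the share with a truly treatment-emergent sign. The documents give neither, so both are assumed, and they are taken as independent. If the maximum counts both, the reported share is 1 − (1 − b)(1 − e). The chance of at least one pre-existing case among n subjects is 1 − (1 − b)^n.

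| b (assumed) | Reported share if e = 0 | Reported share if e = 10% | At least one case, Arm A (n = 8) | At least one case, Arm B (n = 16) |
|---|---|---|---|---|
| 5% | 5% | 14.5% | 34% | 56% |
| 10% | 10% | 19% | 57% | 82% |
| 20% | 20% | 28% | 83% | 97% |
| 30% | 30% | 37% | 94% | 99.7% |

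**7. Would dropping the Visit 2 pre-medication reading be enough?** No. A sign that persists is graded again at Visits 3 to 8 and re-enters the maximum. The grade has to be compared with the Visit 2 value for the same lesion and sign.

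**The case against.** The wrong grade list will probably do little harm. Sites record an integer from 0 to 3, SAP Table 5 is in the same document, and the likely result is an empty grade 4 row. A reader might infer that results will be recoded from 1 to 4, so that a printed grade 3 would mean moderate. Nothing in the documents points to a recode, and the retreatment rule is applied at the site to the recorded grade, so a table label cannot affect it. Nor does a missing grade 0 row by itself make none indistinguishable from not assessed: percentages are required, and grade 0 can be recovered if the denominator is the number assessed. What stands is that 3.7.2 does not state the denominator for these tables.

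On the maximum, the by-visit tables will show how common each sign was before treatment, so baseline is not hidden. That is fair, but it is aggregate information and cannot show whether a given lesion changed.

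The shift tables are limited to six items because those are what is scored minutes after treatment. That explains their content. It does not supply a longer-term comparison for the other signs.

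Finally, the LSR summaries are descriptive, no test or decision rule uses them, and the entry criteria make pre-existing signs less likely. All of that stands, and it limits how serious the point is.

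**Conclusion.** The point holds in two parts of unequal certainty. The grade mismatch is certain from the text and needs correcting in both places, though its likely effect is small. That the all-visit maximum takes in the Visit 2 pre-medication score is the plain reading but not an explicit instruction, so confidence there is moderate. What does not depend on that reading is that pigment change, atrophy and scarring have no within-lesion comparison with baseline anywhere in the LSR analysis, so a pre-existing sign that persists can count as a reaction.

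A reader might infer that the reaction rates will be biased by a known amount, or biased at all. The documents do not support that, because they give no baseline prevalence. The 12.5 and 6.25 points are the weight of one subject at the planned arm sizes, and the wider table rests on assumed prevalences and independence. The finding is a gap in a primary-objective safety display that should be closed, not a demonstrated error in any result.

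**What to change.** In SAP 3.7.2:

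- (a) Replace the 1-to-4 list with grades 0, 1, 2 and 3, for subjects and for lesions, and state that the denominator is the number assessed.
- (b) Define the all-visit maximum as treatment-emergent: count only readings after the first application that exceed the Visit 2 pre-medication grade for the same lesion and the same sign or symptom. Pre-medication readings at later treatment visits stay in, since they follow the first application.
- (c) Add lesion-level shift tables from the Visit 2 pre-medication grade to the maximum post-treatment grade, and to the Visit 8 grade, for hyperpigmentation, hypopigmentation, atrophy and scarring.

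The cost is a wording change and one or two extra tables. All the data are already collected, and trial conduct is unaffected.
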